**PARTNERS HUMAN RESEARCH COMMITTEE
PROTOCOL SUMMARY**

Answer all questions accurately and completely in order to provide the PHRC with the relevant information to assess the risk-benefit ratio for the study. Do not leave sections blank.

PRINCIPAL/OVERALL INVESTIGATOR

[name]

PROTOCOL TITLE

Virtual Reality-based Rehabilitation for Children with Traumatic Brain Injuries

FUNDING

National Institutes of Health

VERSION DATE

Version 5.0 3/22/23

SPECIFIC AIMS

Concisely state the objectives of the study and the hypothesis being tested.

The overall goal of the project is to assess the preliminary efficacy of a novel VR-based interactive cognitive training (VICT) program for cognitive rehabilitation in children with TBI.

Aim 1. Examine VICT's efficacy in improving core and daily EF skills among children with TBI.

Hypothesis 1.1: Children in the intervention group will show enhanced improvement over controls in trained VR-based EF tasks and untrained NIH Toolbox tasks from baseline to post-intervention and follow-up visits;

Hypothesis 1.2: The intervention group will show better reported daily EF than controls at the follow-up visit;

Hypothesis 1.3: Children in the intervention group will show faster improvement than controls in daily-reported EF skills between post-intervention and follow-up visits.

Aim 2. Examine VICT's efficacy in reducing attentional problems among children with TBI.

Hypothesis 2.1: Children in the intervention group will show a greater reduction in attentional problems as measured by testing on the Conners Continuous Performance Test 3rd Edition™ (Conners CPT 3™) from baseline to the post-intervention and follow-up visits than controls;

Hypothesis 2.2: Children in the intervention group will show fewer everyday attentional problems on the Behavior Assessment System for Children 3rd Ed (BASC-3) self- and parent-ratings of attention at the follow-up visit than controls;

Hypothesis 2.3: The direct effect of the VICT program in reducing attention problems will be mediated by children's EF behaviors as measured by the Behavior Rating Inventory of Executive Function, Second Edition (BRIEF2) at the follow-up visit.

Aim 3. Examine VICT's efficacy in improving HRQOL among children with TBI.

Hypothesis 3.1: The intervention group will show higher levels of reported HRQOL than controls at follow-up;

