Hypothesis 3.2: The direct effect of the VICT program on HRQOL at follow-up will be mediated by children's EF skills and ratings of EF behaviors and attention at the post-intervention and follow-up visits.

BACKGROUND AND SIGNIFICANCE

Provide a brief paragraph summarizing prior experience important for understanding the proposed study and procedures.

Traumatic brain injury (TBI) is a leading cause of acquired disability in U.S. children, with an estimated 700,000 cases every year, presenting in 75% of children with trauma and accounting for 70% of deaths from childhood trauma. Childhood TBIs often result in significant impairment in cognitive functions, particularly in core executive functions (EFs) due to the vulnerability of the frontal lobes, especially after a moderate to severe TBI. Core EF is composed of three skills: inhibitory control, working memory, and cognitive flexibility. These skills are associated with impaired EF behaviors, increased attention problems, and lower health-related quality-of-life (HRQOL). However, evidence-based EF rehabilitation programs are lacking. Although a combination of diverse cognitive interventions may improve children's EF, limited affordability, accessibility, adherence, and generalizability hamper clinically adapting and implementing such interventions in the rehabilitation setting. Virtual reality (VR) offers an exciting alternative strategy for EF rehabilitation of childhood TBI due to its flexibility, accessibility, and immersive experiences in three dimensions. These properties may increase adherence to training and foster an enhanced transfer of learned EF skills to untrained tasks in everyday life. *Thus far, rigorous randomized clinical trials (RCTs) have not been conducted to establish the efficacy of VR-based EF rehabilitation for childhood TBI.*

RESEARCH DESIGN AND METHODS

Briefly describe study design and anticipated enrollment, i.e., number of subjects to be enrolled by researchers study-wide and by Partners researchers. Provide a brief summary of the eligibility criteria (for example, age range, gender, medical condition). Include any local site restrictions, for example, "Enrollment at Partners will be limited to adults although the sponsor's protocol is open to both children and adults."

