## **Data Analysis Plan (Updated for 2nd NCE Period)**

First, descriptive analysis will be conducted to compute the means and standard deviations of all predictor and outcome variables listed in the Measures section. Means of baseline covariates, including age, sex, injury severity, recency of injury, verbal intelligence, anxiety, and prior VR gaming experience, will be compared using independent samples t-test between intervention and control groups. Due to the randomization, we expect that most of covariates will show non-significant differences between assignment groups. These variables will be considered balanced between groups and not included as covariates in the analyses that follow. For the covariates that are found imbalanced between groups (perhaps due to the small sample size, they will be controlled statistically in the analyses that follow. This approach will reduce the number of covariates in respective statistical models and maximize the statistical power of each proposed analysis.

Next, hypotheses for each specific aim will be evaluated.

- **Aim 1**
  - *H1.1 and H1.2* will be tested using a *multi-level model* where scores on VR tasks and NIHTB- CB tasks (H1.1) or BRIEF2 scores (H1.2) will serve as respective dependent variables. Study visit (pre, post, follow-up) will serve as a predictor that is nested within subjects and condition will serve as a between-subject predictor.
  - *H1.3* will be tested using a *multi-level model* where time (Day 1 – Day 30) is nested within subjects. The EMA-EF scores will be the DV, allowing each patient to have unique initial level and rate of change in daily EF across the 30-day period.
  - Multi-level models have been used in studies with sample sizes as small as single cases. Therefore, our study with a sample size of 15 will be sufficient to conduct multi-level modeling analyses. Furthermore, in all multi-level models for Aim 1, we will use the Kenward-Roger correction in degrees of freedom^2 to further minimize small sample size bias and prevent inflation of type I error rates in estimation.
- **Aim 2**
  - *H2.1* will be tested using the same approach as H1.1-H1.2 via *multi-level modeling*. Study visit (pre, post, follow-up) will serve as a predictor that is nested within subjects and condition will serve as a between-subject predictor. The only difference is that for this model CPT 3 scores will serve as DV.

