  - *H2.2* will be tested using an *independent samples t-test* with BASC- 3 APS scores at follow-up as DVs and condition as the IV.
  - *H2.3* will be exploratory in nature due to the small sample size. It will be tested using the SPSS Macro for 95% bias-corrected bootstrap mediation analysis with condition as the IV, VR and NIHTB-CB scores at post-intervention/follow-up as mediators, and CPT 3, BASC-3 at follow-up as DVs for each model.
- **Aim 3**
  - *H3.1* will be tested using the same approach as H2.2 via *independent samples t-tests*. The only difference is that for this model PedsQL scores at follow-up will serve as DV.
  - *H3.2* will be similar to H2.3 and exploratory in nature. It be tested using the same mediation analysis as in H2.3, but with PedsQL scores at follow-up as DV instead.

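### The SAP's exploratory H2.3 mediation model omits BRIEF2, the mediator the protocol names, and H3.2 inherits the same incomplete mediator list

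*SAP*

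**What the plan says.** **H2.3.** The protocol (Specific Aims, Hypothesis 2.3) names one mediator of the effect on attention problems: children's "EF behaviors as measured by the Behavior Rating Inventory of Executive Function, Second Edition (BRIEF2) at the follow-up visit". The SAP (Data Analysis Plan, Aim 2, H2.3) plans a bias-corrected bootstrap mediation analysis with condition as the independent variable and "VR and NIHTB-CB scores at post-intervention/follow-up as mediators, and CPT 3, BASC-3 at follow-up as DVs for each model".

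**H3.2.** The protocol (Specific Aims, Hypothesis 3.2) says that the effect on health-related quality of life is mediated by "EF skills and ratings of EF behaviors and attention at the post-intervention and follow-up visits". The SAP (Aim 3, H3.2) says: "It be tested using the same mediation analysis as in H2.3, but with PedsQL scores at follow-up as DV instead".

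**Status.** The SAP says that H2.3 "will be exploratory in nature due to the small sample size" and that H3.2 "will be similar to H2.3 and exploratory in nature".

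**BRIEF2 elsewhere.** In the SAP text available, BRIEF2 appears only under Aim 1, as an outcome: "or BRIEF2 scores (H1.2) will serve as respective dependent variables". The protocol's Visit 3 list includes both the self-report and the parent-report BRIEF2.

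**The concern.** A mediation analysis is defined by its mediator. If the protocol asks whether rated everyday EF behavior carries the effect on attention, and the SAP models test performance instead, then a result reported under H2.3 answers a different question from the one stated. A null result could be read as evidence against a BRIEF2 pathway that was never examined. A positive result could be read as support for it.

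For H3.2, the planned model would speak to one of the pathways the protocol names and say nothing about the others.

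There is also a reporting risk. With two documents naming different mediators, the choice between them could be made after results are seen. Settling it beforehand removes that doubt.

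**Working it through.** No figure in the plan needs reproducing, and no power or error-rate calculation applies. The check is to set the named variables side by side.

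1. **H2.3 mediators.** Protocol: {BRIEF2 at follow-up}. SAP: {VR scores, NIHTB-CB scores}, at post-intervention/follow-up. Overlap: 0 of the 1 mediator the protocol names.

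2. **Are these two names for one construct?** The protocol treats them as different. Hypothesis 1.1 concerns VR and NIH Toolbox tasks, while Hypothesis 1.2 concerns reported daily EF. Hypothesis 3.2 lists EF skills and ratings of EF behaviors as separate items. VR and NIHTB-CB scores therefore do not stand in for BRIEF2.

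3. **Could BRIEF2 have been dropped for lack of data?** The documents do not suggest so. Self-report and parent-report BRIEF2 are both scheduled at Visit 3, the visit named in Hypothesis 2.3.

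4. **H3.2 mediators.** Protocol: {EF skills, EF-behavior ratings, attention}. The only change the SAP states from H2.3 is the dependent variable, so the mediators carry over as {VR, NIHTB-CB}. Taking EF skills to mean these performance tasks, as the contrast with ratings implies, coverage is 1 of 3 groups.

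5. **What does attention mean in Hypothesis 3.2?** The phrase can mean ratings of attention, which points to BASC-3. It can also mean attention in general, which would admit CPT 3, the attention test in Hypothesis 2.1. The documents do not settle this. Under either reading, no attention measure is a mediator in SAP H3.2.

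6. **Which visits could supply the missing mediators?** At follow-up, BRIEF2, BASC-3 and CPT 3 are all listed. At post-intervention, BRIEF2 is implied by the protocol's endpoint definition and by the SAP's visit factor for H1.2. CPT 3 is implied by Hypothesis 2.1 and by the visit factor for H2.1. BASC-3 at post-intervention is not established: the Visit 1 questionnaires are not named, Visit 2 is described as repeating the baseline tasks, and the parent payment is tied to questionnaires at follow-up.

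7. **What is unaffected?** H1.1 to H1.3, H2.1, H2.2 and H3.1 do not use the mediation models. The study endpoint is defined by changes in VR, NIH Toolbox and BRIEF2 scores and does not include mediation.

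**The case against.** **The analyses are only exploratory.** This is true, and it limits severity. But the reason the SAP gives for the label is small sample size, which does not account for a different mediator. Exploratory results are still reported under a hypothesis number, and the model should match that hypothesis.

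**The explanation may lie in text not seen.** The SAP refers to "all predictor and outcome variables listed in the Measures section", and that section was not available, nor was the part of the SAP before the Data Analysis Plan. The plan is also headed as updated for a second NCE period, so the change may be deliberate. This stands as a limit on confidence: a reader might infer an unexplained abandonment of the protocol hypothesis, and the available text does not establish that. It does not remove the mismatch, because the Data Analysis Plan assigns the mediators explicitly.

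**Performance scores may be the better mediators.** VR and NIHTB-CB at post-intervention precede the follow-up outcomes, whereas BRIEF2 at follow-up does not. That could justify a deliberate change, but the documents do not give it as a reason. It also covers only part of the SAP's model, which allows mediator scores from follow-up, the same visit as the outcomes.

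**A stronger reading of H3.2.** A reader might infer that the SAP leaves the H3.2 mediators unspecified, with only the method carrying over. The wording does not support that: one change is stated, to the outcome, and the natural reading keeps the mediators. The fault is an incomplete list. A reader might also count which rating instruments are available at which visit and treat the total as the size of the problem. Such a count assumes that attention means BASC-3 alone, which the protocol does not say.

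**Conclusion.** The point holds as a minor inconsistency. For H2.3, the SAP lists none of the single mediator the protocol names. H3.2 inherits the same list and covers one of three mediator groups, leaving out EF-behavior ratings and attention. No efficacy estimate and no main comparison changes.

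Confidence is high that the two documents name different mediators. Whether the difference is explained elsewhere depends on SAP text that was not available. The one-of-three count also assumes that EF skills in Hypothesis 3.2 means the VR and NIH Toolbox tasks.

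**What to change.** Reconcile the documents before unblinded analysis, in one of two ways.

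- **Align the SAP with the protocol.** For H2.3, name BRIEF2 at follow-up as the mediator, state whether self-report, parent report or both are used, and keep VR/NIHTB-CB as a labelled additional analysis. For H3.2, add BRIEF2 and an attention measure to the EF-skill mediators. State whether attention means BASC-3 ratings, CPT 3 or both, and use each measure only at visits where it was collected.
- **If the change was deliberate, amend the hypotheses.** Reword H2.3 and H3.2 to match the SAP and give the reason.

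Under either route, state which visit's mediator score enters each model, and that a mediator measured at the same visit as the outcome does not establish temporal order. Where BRIEF2 is the mediator and BASC-3 the outcome, or both are mediators, note that the same child or parent may have completed both, so part of their association may reflect a shared rater.

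The first route costs SAP wording and a changed variable list in the same macro. It needs no new follow-up data, but the team should first confirm which forms were given at post-intervention. The added intervals come from the SAP's stated sample of 15 and should be reported descriptively. The second route costs protocol wording and a stated reason.

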the baseline assessment, as well as VR experience questions such as motion sickness, perceived benefits and challenges, and physical exertion.

Between Visit 2 and Visit 3:

- A brief EMA-EF Survey will be sent to participants to complete daily between the post-intervention and follow-up visits, which may take about 2 minutes per day for 30 days.

Visit 3:

Follow-Up Visit

- Follow-up visits are scheduled 30 days following the post-intervention assessment (up to 12 months). Staff blinded to the participants' group assignment will administer the following measures:
 - VR and NIH Toolbox tests;
 - Conners CPT 3;
 - Children's Anxiety Meter;
 - Self-report BRIEF2, BASC-3, and PedsQL Generic Core Scales;
 - TPVT
 - Media Use Survey.
 - A parent will complete the parent-report version of BRIEF2, BASC-3, and PedsQL.

The study endpoint is the preliminary efficacy of the VICT program, defined as the changes in VR Assessment Scores, NIH Toolbox Composite Scores, and BRIEF2 Global Scores between baseline and post-intervention and between baseline and follow-up assessment.

For studies involving treatment or diagnosis, provide information about standard of care at Partners (e.g., BWH, MGH) and indicate how the study procedures differ from standard care. Provide information on available alternative treatments, procedures, or methods of diagnosis.

The virtual reality intervention is designed to be supplementary to standard of care at Spaulding Rehabilitation Hospital. Therefore, all participants will still receive standard of care as determined by their doctors regardless of participation of this study or random assignment to the intervention or control group.

Describe how risks to subjects are minimized, for example, by using procedures which are consistent with sound research design and which do not unnecessarily expose subjects to risk or by using procedures already being performed on the subject for diagnostic or treatment purposes.

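### Protocol H2.3 requires, and SAP H2.3 and H3.2 permit, a mediator measured at the same visit as the outcome; the plan should make the Visit 2 mediator the main one and call same-visit models associations

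*SAP*

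**What the plan says.** - **Protocol, Specific Aims, H2.3.** The effect on attention problems is to be mediated by EF behaviours "as measured by the Behavior Rating Inventory of Executive Function, Second Edition (BRIEF2) at the follow-up visit". No earlier visit is named.
- **Protocol, Specific Aims, H3.2.** The effect on HRQOL at follow-up is to be mediated by "EF skills and ratings of EF behaviors and attention at the post-intervention and follow-up visits". Both visits are named.
- **SAP, Data Analysis Plan, Aim 2, H2.3.** The method is a "95% bias-corrected bootstrap mediation analysis with condition as the IV", with "VR and NIHTB-CB scores at post-intervention/follow-up as mediators, and CPT 3, BASC-3 at follow-up as DVs for each model".
- **SAP, Aim 3, H3.2.** The same mediation analysis, "but with PedsQL scores at follow-up as DV instead".
- **Status.** H2.3 "will be exploratory in nature due to the small sample size"; H3.2 is likewise called exploratory.
- **Earlier EF measures.** Visit 2 repeats the baseline tasks within a week of the intervention session. After it, "A brief EMA-EF Survey will be sent to participants to complete daily between the post-intervention and follow-up visits", for 30 days. Visit 3 is set for 30 days after Visit 2, up to 12 months.

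The SAP gives no rule on time order, no baseline adjustment specific to the mediation models, and no caveat on reverse influence.

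**The concern.** H2.3 and H3.2 describe a sequence: training improves EF, and better EF then improves attention or quality of life. When mediator and outcome are taken at one visit, the data cannot show which came first. A gain in attention that lifts EF scores yields the same product of paths as a gain in EF that lifts attention.

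A second route applies where both measures are ratings. BRIEF2, BASC-3 and PedsQL are all completed at Visit 3 by the child and by a parent, so two of them may partly record the same thing. This touches protocol H2.3 (BRIEF2 against attention ratings) and the rating mediators of protocol H3.2. It does not touch the SAP's mediators, which are performance tests.

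The slash in the SAP wording can mean separate models, joint mediators or alternatives. A team following the plan to the letter could therefore run only the same-visit model and report it as mediation, although ordered measurements are available.

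**Working it through.** The documents give no effect size, correlation or target indirect effect for the mediation models, so there is no planned figure to reproduce. All inputs below except N are assumptions. X is condition, M mediator, Y outcome; a is the X-to-M effect, b is the M-to-Y slope given X, and within-arm variances are 1.

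**1. Timing, side by side**

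| Hypothesis | Mediator and visit | Outcome visit | Ordered? |
|---|---|---|---|
| Protocol H2.3 | BRIEF2, follow-up | BASC-3 (H2.2) and SAP H2.3 outcomes: follow-up | No |
| SAP H2.3 | VR, NIH Toolbox, post-intervention/follow-up | Follow-up | Only with the Visit 2 mediator |
| Protocol H3.2 | EF skills and ratings, both visits | Follow-up | Only with the Visit 2 mediator |
| SAP H3.2 | As SAP H2.3 | Follow-up | Only with the Visit 2 mediator |

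**2. Same visit, outcome causes mediator, no M-to-Y path**

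Y = tau·X + e and M = rho·Y + sqrt(1 − rho²)·u. Then a = rho·tau, b = rho and the total effect is tau, so the false proportion mediated is ab/tau = rho².

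| rho | 0.2 | 0.3 | 0.5 | 0.6 | 0.7 | 0.8 |
|---|---|---|---|---|---|---|
| rho² | 4% | 9% | 25% | 36% | 49% | 64% |

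**3. Same visit, two equally loaded ratings of one treated construct**

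With T = d·X + e, let Y and M each equal sqrt(rho)·T plus independent error. Then a = sqrt(rho)·d, b = rho, the total is sqrt(rho)·d, and the proportion is rho itself. This applies only to the protocol's rating mediators.

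**4. When there is no false effect**

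If M and Y share only a cause that treatment does not change, a = 0 and ab = 0, however strongly they correlate.

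**5. How often the planned interval would exclude zero**

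A simulation used a 95% bias-corrected bootstrap with 1,000 resamples and 1,000 trials per cell. Assumed inputs were an effect d of 0.5 to 0.8 SD and r of 0.5 to 0.7, where r is the path strength in the reverse case and the common-factor share of variance in the other two. N was 15 (SAP) or 32 (protocol).

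| Situation, no true mediation | N = 15 | N = 32 |
|---|---|---|
| Same visit, outcome drives mediator | 7–23% | 14–41% |
| Same visit, two ratings of one construct | 8–30% | 17–54% |
| Visit 2 mediator not moved by treatment (a = 0) | 6–9% | 7–9% |

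The last row illustrates step 4. It does not isolate the effect of timing.

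**6. What a Visit 2 mediator does and does not cure**

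Suppose attention has already changed by Visit 2 (Y2), drives EF then (M2 = rho·Y2 + error), and persists: Y3 = s·Y2 + error. Then a = rho·tau, b = s·rho and the total is s·tau, so ab/total is again rho².

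Now adjust for baseline, assuming a baseline-to-Visit 2 stability of 0.7 and s = 0.8. The proportion becomes rho²v/(rho²v + 1 − rho²), where v is the outcome variance left after baseline at the mediator's visit.

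- Visit 2 mediator: v = 1 − 0.7² = 0.51. At rho = 0.5 this gives 0.1275/0.8775 = 15%; at 0.8, 0.3264/0.6864 = 48%.
- Follow-up mediator: v = 1 − (0.7 × 0.8)² = 0.6864. At rho = 0.5 this gives 0.1716/0.9216 = 19%; at 0.8, 0.4393/0.7993 = 55%.

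Adding Y2 to the outcome model makes b = 0 in this scenario, because M2 tells nothing about Y3 beyond Y2. Numerical evaluation of the same model agreed with these results.

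**The case against.** **The lagged mediator is already in the plan.** This stands. A reader might infer that the mediation aims as a whole take mediator and outcome at one visit. SAP H2.3 and protocol H3.2 both name post-intervention, so only protocol H2.3 is confined to follow-up. The fault elsewhere is that nothing says which visit governs.

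**Rating overlap does not describe the SAP models.** This stands too: VR and NIH Toolbox scores are tests, not ratings. Reverse influence still applies to them at follow-up.

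**Correlation alone does not create a false indirect effect.** Correct, by step 4. It is tempting to say that any same-visit correlate will look like a mediator, but treatment must also move the mediator, through the outcome or a shared treated construct.

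**Moving the mediator to Visit 2 may not help.** Partly right. Step 6 shows the same rho² if attention changed early and persisted. Baseline adjustment reduces it only modestly, so adjustment for the Visit 2 outcome is needed as well. Confounding of mediator and outcome also remains, because the mediator is not randomised.

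**The analyses are exploratory.** This limits the consequence. Neither hypothesis is part of the protocol's study endpoint, and nothing in the documents says a same-visit result would be presented as an established mechanism. But the SAP gives sample size as the reason for the label. Reverse influence is a bias that more children would not remove; in step 5 the false-positive rates are higher at N = 32 than at N = 15.

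**Conclusion.** The point holds in limited form. Protocol H2.3 requires a same-visit mediator, and the SAP permits one for H2.3 and H3.2 without a time-order rule, so following the plan can yield a cross-sectional association reported under the name of mediation. If the outcome drives the mediator, the false proportion mediated is about 4% to 64% for an assumed within-arm rho of 0.2 to 0.8. It is zero if treatment does not move the mediator. No correlation is given in the documents, so these figures show scale and are not estimates for this trial.

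The documents do not support concluding that every mediation model is concurrent, or that a Visit 2 mediator would by itself establish mechanism. Since both hypotheses are exploratory, this is an inexpensive improvement to the plan and does not bear on the study endpoint.

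**What to change.** 1. In the SAP, replace the slash with a rule: the main H2.3 and H3.2 models use Visit 2 VR and NIH Toolbox scores as mediators, with CPT 3, BASC-3 and PedsQL at follow-up as outcomes.
2. Adjust for the baseline mediator and baseline outcome where they are collected.
3. As a sensitivity analysis, add the Visit 2 value of the outcome to the outcome model where it exists. CPT 3 qualifies, since SAP H2.1 models it at all three visits. The protocol's visit schedule names BASC-3 and PedsQL only at Visit 3, so their earlier collection must be confirmed. Keep this as a sensitivity analysis, because it can also remove genuine mediation that was complete by Visit 2.
4. Label any model with a follow-up mediator as a cross-sectional association.
5. Amend protocol H2.3 and H3.2 and the SAP so that they agree on mediator and visit. At present protocol H2.3 names BRIEF2 and the SAP names VR and NIH Toolbox scores.
6. For everyday EF, mean EMA-EF over the diary days before follow-up may be added as a secondary mediator, or Visit 2 BRIEF2 if its collection is confirmed. The endpoint definition and the three-visit model for SAP H1.2 imply it, but the schedule names BRIEF2 only at Visit 3. EMA-EF has no described pre-intervention value and is already the H1.3 outcome.
7. State that time ordering does not remove mediator-outcome confounding.

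The cost is wording in the SAP and two hypotheses, with no new data. Earlier mediators may show a smaller indirect effect, and each added covariate costs precision at N of about 15.

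### The exploratory mediation models for H2.3 and H3.2 have no baseline EF, attention or HRQOL term, so pre-existing impairment can appear as mediation if training moves EF

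*SAP*

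**What the plan says.** Under Aim 2 of the Data Analysis Plan, H2.3 uses the "SPSS Macro for 95% bias-corrected bootstrap mediation analysis with condition as the IV", with "VR and NIHTB-CB scores at post-intervention/follow-up as mediators, and CPT 3, BASC-3 at follow-up as DVs for each model". Under Aim 3, H3.2 is to be "tested using the same mediation analysis as in H2.3, but with PedsQL scores at follow-up as DV instead". Neither entry names a baseline score. H2.3 "will be exploratory in nature due to the small sample size", and H3.2 is also labelled exploratory.

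Covariates are handled at the start of the same section. "Means of baseline covariates, including age, sex, injury severity, recency of injury, verbal intelligence, anxiety, and prior VR gaming experience" are compared between arms by t-test. Where no significant difference is found, "These variables will be considered balanced between groups and not included as covariates in the analyses that follow"; only those found imbalanced are controlled. Injury severity is on this list. Baseline EF, CPT 3, BASC-3 and PedsQL scores are not.

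Baseline EF and attention scores will nevertheless exist. The protocol's Visit 1 tests cognition and attention before randomisation. Hypothesis 1.1 concerns "untrained NIH Toolbox tasks from baseline to post-intervention and follow-up visits", and Hypothesis 2.1 needs baseline CPT 3 in the same way.

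**The concern.** In a mediation model the indirect effect is the product of two slopes: condition to mediator (a), and mediator to outcome given condition (b). Randomisation makes a unconfounded. It does nothing for b, because nobody randomised the children to their EF scores.

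The trial enrols moderate to severe TBI, and the protocol's Background links core EF skills to attention problems and HRQOL. A child who is more impaired at entry can be expected to score worse on EF after training and worse on attention or HRQOL at follow-up, whatever the training did. Without a baseline term, b absorbs that shared cause. Any arm effect on EF is then multiplied by a slope that partly reflects the child's starting point, and the direct effect is biased by the same amount in the opposite direction.

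The covariate rule looks for the wrong thing. A between-arm t-test asks whether condition is confounded. A common cause of mediator and outcome confounds b even when the arms are perfectly balanced. At stake is the claim that training works through EF, in a study whose findings are meant to guide further development of the intervention.

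**Working it through.** The plan gives no effect size, correlation or power figure for the mediation models, so there is no stated figure to reproduce.

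**Inputs from the documents.** 95% bias-corrected bootstrap (SAP, H2.3); 1:1 allocation (Protocol, Visit 1); N=15 (SAP, Aim 1) and N=32 (Protocol, Research Design and Methods).

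**Assumptions, not in the documents.** True effect of EF on outcome is 0. Baseline EF (U) is the only common cause and is measured without error. U correlates r1 with the mediator and r2 with the outcome within arm. The arm shifts EF by a SD. The outcome is scaled so that higher is better.

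**Large-sample bias.** Let M = a·X + r1·U + error and Y = r2·U + error, each with unit variance within arm.

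- Slope of Y on M given X, without U: b = r1 × r2 = 0.7 × 0.5 = 0.35, where the truth is 0.
- Spurious indirect effect at a = 1: 1 × 0.35 = 0.35 SD.
- Direct effect: total − indirect = 0 − 0.35 = −0.35 SD.
- At a = 0.5 the spurious indirect effect is 0.5 × 0.35 = 0.175 SD. With r1/r2 of 0.5/0.3 it is 0.5 × 0.15 = 0.075 SD.
- At a = 0 it is 0.

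**How often the planned interval falsely excludes zero** (simulation, bias-corrected bootstrap; repeat runs agree to within a few percentage points):

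| Arm effect on EF | r1 / r2 | Model | N=15 | N=32 |
|---|---|---|---|---|
| 1 SD | 0.7 / 0.5 | no baseline term | 20–23% | 49% |
| 1 SD | 0.7 / 0.5 | baseline EF in both equations | about 7% | about 10% |
| 1 SD | 0.5 / 0.3 | no baseline term | 9% | 18% |
| 1 SD | 0.8 / 0.7 | no baseline term | 39% | 78% |
| 0.5 SD | 0.5/0.3 to 0.7/0.5 | no baseline term | 3–8% | 11–22% |

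**Does the SAP's balance rule help?** At N=15 (7 v 8, 13 df) the observed arm difference must reach 2.16 × √(1/7 + 1/8) = 1.12 SD to be significant. A second simulation made injury severity the common cause, with a within-arm mediator–outcome correlation of 0.3 or 0.5 and arm effects of 0.5 to 1.2 SD. The severity test was significant in only 3–6% of trials. Under the SAP rule the interval falsely excluded zero in 6.5–40% of trials at N=15 and 19–79% at N=32. With no adjustment at all the figures were 7–41% and 20–83%, so the rule changes almost nothing.

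**Does baseline adjustment help when baseline is only a proxy?** In that second simulation, always entering baseline mediator and baseline outcome cut the rates to 2–7% at N=15 and 5–11% at N=32. The large-sample slope fell from 0.30 to 0.07, or from 0.50 to 0.10. Most of the bias goes, but not all.

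**The case against.** **The analyses are exploratory.** This stands as a limit on the consequences: the protocol's stated endpoint is change in VR, NIH Toolbox and BRIEF2 scores, and nothing in it depends on these models. But the SAP gives small sample size as the reason for the label. That speaks to precision. The bias does not shrink with more children, and the false-positive rate rises from N=15 to N=32.

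**Severity is not ignored.** This is correct. It is a listed covariate, and a reader who inferred that the plan overlooks it would be wrong. What fails is the trigger for using it, for the reason given above.

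**The size depends on an arm effect the documents do not state.** This also stands. The minimum exposure is one 30-minute session, and a 1 SD shift in EF may be generous. At 0.5 SD and N=15, the SAP's own sample size, a false declaration is uncommon. If training does not move EF there is no systematic bias in the indirect effect.

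**Baseline adjustment is not a cure.** This is true as well. A residual slope of about 0.07–0.10 remained when severity was the true common cause.

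**The plan may adjust elsewhere.** The SAP text ahead of the Data Analysis Plan was not available, so a baseline adjustment described there cannot be ruled out. The mediation entries themselves neither name one nor refer to one.

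**Conclusion.** The concern holds in a limited form. As written, the H2.3 and H3.2 models leave the mediator-to-outcome path confounded by the child's condition at entry, and the covariate rule does not repair it. If training moves EF, pre-existing impairment can appear as mediation when EF has no effect on attention or HRQOL. Under the main assumed scenario the spurious indirect effect is about 0.35 SD, with a false declaration in about one trial in five at N=15 and about one in two at N=32. Under weaker assumptions at N=15 the rate falls to 3–8%.

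A reader might infer that these models will show mediation whatever happens, or that a positive result must be false. The documents support neither reading. The bias needs both an arm effect on EF and a shared cause, and even in the main scenario most trials of 15 would declare nothing. The correlations and arm effects are assumptions; the direction of the problem is not. This is worth correcting before analysis, but it does not threaten the trial's stated endpoint.

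**What to change.** In H2.3 and H3.2, always enter the baseline value of the mediator in both the mediator and the outcome equation, regardless of the balance t-tests. Enter the baseline value of the outcome in both equations too, where it is collected. CPT 3 is collected at baseline. Baseline collection of BASC-3 and PedsQL should be confirmed, since the protocol's remuneration text ties the parent questionnaires to the follow-up visit. Add a sentence that any mediation result rests on there being no remaining common cause of mediator and outcome.

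The cost is a few lines of SAP wording, one or two degrees of freedom per equation, and no new data for EF and CPT 3. At N=15 there is little room for further covariates. The adjustment reduces the bias but does not fully remove it if baseline scores are measured with error or other common causes remain, so the stated assumption is needed as well as the covariates.
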